## 5. SELECTION OF CLINICAL SPECIMENS FOR TESTING

### **5.1. Inclusion criteria**

1. Nasopharyngeal or saliva specimens of patients in Queen Mary Hospital of Hong Kong
2. Tested for influenza A virus using a commercially available assay or by the Public Health Laboratory Services Branch in Hong Kong

### **5.2 Exclusion criteria**

1. Insufficient specimen volume

## 6. STUDY PROCEDURES

### **6.1 Nucleic acid extraction and real-time reverse transcription-polymerase chain reaction (RT-PCR) for influenza A virus**

Saliva and nasopharyngeal specimens will be subjected to total nucleic acid (TNA) extraction by NucliSENS easyMAG (BioMerieux, Boxtel, Netherlands) as we described previously [10]. Briefly, 250 µL of each specimen will be mixed with lysing buffer. After extraction, the nucleic acids will be recovered using 55 µL of elution buffer.

Monoplex real-time RT-PCR assays for influenza A virus will be performed using QuantiNova Probe RT-PCR Kit (QIAGEN, Hilden, Germany). The reagent mixture (20 µL) will contain 1x QuantiNova Probe RT-PCR Master Mix, 1x QN Probe RT-Mix, 0.8 µM of each forward and reverse primer, 0.2 µM of probe and 5 µL of TNA as the template. The thermal cycling conditions will be 10 min at 45 °C for reverse transcription, 5 min at 95 °C for PCR initial activation, and 50 cycles of 5 s at 95 °C and 30 s at 55 °C. All reactions will be performed using the LightCycler 480 Real-Time PCR System (Roche, Basel, Switzerland). The primers and probes for the M gene RT-PCR have been published by the WHO and the US CDC [5, 6].

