## 1. PROTOCOL SYNOPSIS

Protocol title	Evaluation of novel molecular assays for the detection of influenza virus
Hypothesis	Our novel molecular assays for the detection of influenza A virus will be non-inferior to current molecular assays published by the World Health Organization and the US Centers for Disease Control and Prevention
Primary objective	To evaluate the sensitivity and specificity of different molecular assays
Clinical specimens	Nasopharyngeal and saliva specimens previously tested for influenza A virus
Study design	We will randomly retrieve archived nasopharyngeal and saliva specimens that were previously tested for influenza A virus using commercially available assays in our laboratory, tested for influenza A virus at the Public Health Laboratory Service Branch in Hong Kong. These specimens will be tested for influenza A virus by 4 different RT-PCR assays as listed below: 

1. Our new RT-PCR assay targeting PB2 gene

2. Our new RT-PCR assay targeting NS gene

3. M gene RT-PCR published by the World Health Organization

4. M gene RT-PCR published by the US CDC.

Primary outcome	Results of different RT-PCR assays
Secondary outcome	Cycle threshold (Ct) value of different RT-PCR assays
Data analysis	Sensitivity, specificity, positive predictive value and negative predictive value will be determined

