## 2. BACKGROUND

Seasonal influenza virus causes an estimated 0.3-0.6 million deaths per year. Avian influenza virus H5N1, H7N9 and H5N6 has fatality rate of over 30% [1-3]. Swine influenza viruses from pigs have also infected humans [4].

Molecular assays are now used routinely in the detection of influenza viruses. The M gene is often used as the target for all influenza A viruses because the nucleotide sequence of this gene is relatively conserved among all the influenza A viruses. The World Health Organization and the US Centers for Disease Control and Prevention (CDC) have published protocols for molecular detection of influenza A virus M gene [5, 6].

However, recent studies have shown that mutations in the M gene have led to a reduced sensitivity of RT-PCR assay targeting this gene [7, 8]. Therefore, it is important to use

alternative conserved genes as the target of RT-PCR. In this study, our aim is to evaluate two new RT-PCR assays that are based on PB2 and NS gene segment.

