### **4. STUDY DESIGN**

#### **4.1. Overall study design**

We will randomly retrieve archived nasopharyngeal and saliva specimens that were previously tested for influenza A virus using commercially available assays in our laboratory, tested for influenza A virus at the Public Health Laboratory Service Branch in Hong Kong. These specimens will be tested for influenza A virus by 4 different RT-PCR assays as listed below:

1. Our new RT-PCR assay targeting PB2 gene
2. Our new RT-PCR assay targeting NS gene
3. M gene RT-PCR published by the World Health Organization
4. M gene RT-PCR published by the US CDC.

Sensitivity and specificity will be determined as we described previously [9].

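### Does running the WHO and CDC M gene assays under one common kit and cycling profile change the comparators named in the hypothesis?

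*Protocol*

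**What the plan says.** The comparators are described at three levels of detail.

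- **Protocol, Section 1 (Hypothesis):** the new assays "will be non-inferior to current molecular assays published by the World Health Organization and the US Centers for Disease Control and Prevention". Sections 1 and 4.1 list the comparators accordingly, for example "M gene RT-PCR published by the World Health Organization", with the US CDC assay named in the same way.
- **Protocol, Section 2:** WHO and the US CDC "have published protocols for molecular detection of influenza A virus M gene", with references 5 and 6 cited.
- **Protocol, Section 6.1:** "Monoplex real-time RT-PCR assays for influenza A virus will be performed using QuantiNova Probe RT-PCR Kit". The section gives one extraction method, one reaction mix (0.8 µM of each primer, 0.2 µM of probe), one profile of 50 cycles with a 55 °C step, and one real-time instrument. It makes no exception for the M gene assays. On what comes from the two bodies it says: "The primers and probes for the M gene RT-PCR have been published by the WHO and the US CDC", again citing references 5 and 6.

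The Protocol does not reproduce the published reaction conditions, and it does not say whether those in Section 6.1 follow them.

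**The concern.** An RT-PCR assay consists of its oligonucleotides and the conditions under which they are used. The hypothesis names whole assays, while Section 6.1 attributes only the oligonucleotides to WHO and CDC and puts all four targets through one reaction set-up. One profile could be native to both M gene assays only if their published conditions coincide, which the Protocol does not claim.

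The direction of a possible error matters here. In a non-inferiority comparison, sensitivity lost by the comparator moves the observed difference towards the conclusion the investigators hope for. If such a loss occurred, a favourable result would support a statement about the WHO and CDC primer-probe sets under this laboratory's conditions, and a statement about the published assays would go too far. The secondary outcome, the Ct value, also depends on reaction conditions.

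**Working it through.** The Protocol gives no figure on this point to reproduce. The check compares the sections, followed by a bound on what an assumed effect would mean.

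**Step 1. What is named and what is run.** Sections 1 and 4.1 name published assays, Section 2 speaks of published protocols, and Section 6.1 credits primers and probes. The wording does narrow from one place to the next, so the ambiguity of scope is real.

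**Step 2. Is a departure from the published conditions shown?** That would need the kit, concentrations and cycling in references 5 and 6. The Protocol does not give them, so the answer is no. That one profile is unlikely to suit two protocols exactly is a reasonable suspicion, but it does not tell us which comparator departs, if either does, or by how much.

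**Step 3. Are the new assays favoured by the set-up?** The kit, extraction system and instrument are all commercial products. Nothing says the PB2 and NS assays were developed or tuned on this kit and profile, so a home advantage is not documented.

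**Step 4. Size, under assumptions only.** Section 7.1 gives 80 + 80 = 160 specimens previously positive for influenza A. Let *d* be the change in comparator sensitivity caused by the common conditions; the observed difference (new minus comparator) then shifts by −*d*. For an assumed range:

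| *d* (points) | Shift in difference | Specimens out of 160 |
|---|---|---|
| −5 | +5 | 0.05 × 160 = 8 |
| −2 | +2 | 0.02 × 160 = 3.2 |
| 0 | 0 | 0 |
| +2 | −2 | 3.2 |
| +5 | −5 | 8 |

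Against an assumed margin of 5 points, a loss of 2 to 5 points would use 2/5 = 40% to 5/5 = 100% of it. The Protocol states neither a loss nor a margin, so these percentages divide one assumption by another. The lower half of the table is as compatible with the text as the upper half.

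**Step 5. What would the alternative cost?** Running each comparator under its own published conditions needs two further cycling profiles and possibly other reagents. Target gene and chemistry would then vary together: a difference between PB2 and an M gene assay could come from either, and Ct values from different chemistries would be harder to compare. Section 2 motivates the study by M gene mutations that reduce detection. A common set-up, in which only target and oligonucleotides differ, addresses that question more directly.

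**The case for a change.** The best argument for a change is that the definition of the comparator belongs in the protocol and cannot be left to a SAP. Section 6.1 is the only definition the new assays have, so they cannot be run off specification; only the comparators can. Rewording the hypothesis to speak of WHO and CDC M gene primer-probe sets under common study conditions would cost nothing but a narrower claim, and it would keep a report from claiming more than the procedure supports.

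Part of this stands. The label in Sections 1 and 4.1 is looser than the procedure, and a careful report should state the conditions next to any non-inferiority claim. The rest does not carry enough weight. The asymmetry shows that harm is possible, without showing that it occurs. The reaction conditions and the source of the oligonucleotides are set out openly in Section 6.1, so a reader can see what was compared. Rewording would leave every specimen, reaction and planned estimate as it is.

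**Conclusion.** No change to the plan is needed. The mismatch in wording between Sections 1 and 4.1 on one side and Section 6.1 on the other is real but minor. A wrong comparator is not demonstrated, and neither the direction nor the size of any bias can be derived from the Protocol. The 3.2 to 8 specimens out of 160 rest wholly on an assumed loss of 2 to 5 points. Running all four assays under common conditions is a fair trade-off: it gives up some fidelity to the published protocols and gains a cleaner comparison of gene targets and of Ct values.

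This judgement assumes that the results will be reported with the conditions that Section 6.1 discloses. It would need revisiting if references 5 and 6 showed that the common conditions differ materially from the published ones in a way known to reduce M gene sensitivity.

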## 7. STATISTICAL METHODS

### **7.1 Sample size**

We will perform all 4 RT-PCR assays on a total of 320 specimens, including

- 80 nasopharyngeal specimens which tested positive for influenza A by commercially-available molecular assays or by testing performed at the Public Health Laboratory Services Branch in Hong Kong
- 80 nasopharyngeal specimens which tested negative for influenza A by commercially-available molecular assays or by testing performed at the Public Health Laboratory Services Branch in Hong Kong

- 80 saliva specimens which tested positive for influenza A by commercially-available molecular assays
- 80 saliva specimens which tested negative for influenza A by commercially-available molecular assays

The sample size is based on feasibility of the study

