## **7.2 Analysis of the study**

Sensitivity, specificity, positive predictive value and negative predictive value will be calculated for

1. All specimens
2. Nasopharyngeal specimens only
3. Saliva specimens only

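### Could a nasopharyngeal specimen with discordant prior results be filed as a reference-negative under section 7.1?

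*Protocol*

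**What the plan says.** Section 7.1 sets four groups of 80 specimens, 320 in all. The nasopharyngeal positives are "80 nasopharyngeal specimens which tested positive for influenza A by commercially-available molecular assays or by testing performed at the Public Health Laboratory Services Branch" and the nasopharyngeal negatives are "80 nasopharyngeal specimens which tested negative for influenza A by commercially-available molecular assays or by testing performed at the Public Health Laboratory Services Branch". The two saliva groups are defined by commercial molecular assays alone, with the noun in the plural.

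Section 5.1 admits specimens "Tested for influenza A virus using a commercially available assay or by the Public Health Laboratory Services Branch in Hong Kong". Section 5.2 has a single exclusion, "Insufficient specimen volume". Section 4.1 and the synopsis describe the prior testing without a conjunction between the sources: "using commercially available assays in our laboratory, tested for influenza A virus at the Public Health Laboratory Service Branch in Hong Kong".

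Section 7.2 calculates the four accuracy measures for all specimens and for each specimen type, but names no reference standard. Section 4.1 refers to an earlier publication for how sensitivity and specificity are determined.

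**The concern.** The logical complement of being positive by either source is being negative on every test done. Section 7.1 asks only for a negative by either source. A specimen positive at one source and negative at the other therefore qualifies for both groups, and could be drawn as a negative although another test had already found influenza A. Neither the inclusion nor the exclusion criteria give a precedence rule, and the bare comma in section 4.1 and the synopsis could be taken to mean that both tests were done.

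Sensitivity and specificity are the only objective, and the hypothesis compares new assays with M-gene assays. The background motivates the new assays by reports that "mutations in the M gene have led to a reduced sensitivity of RT-PCR assay targeting this gene". A specimen found by the PB2 or NS assay and missed by an M-gene assay would count in favour of the new assay if labelled positive, and against it if labelled negative. If the archived label serves as the reference, the choice of label sets the direction of the comparison for that specimen.

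**Working it through.** **Inputs.** From section 7.1: 80 positives and 80 negatives for each specimen type. Total: 4 × 80 = 320, which agrees with the protocol. The size rests on feasibility, so there is no power calculation to reproduce. The number of discordant specimens, d, is not given; the values below are assumed.

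**Which specimens meet both definitions?** Take each possible pair of prior results (commercial assay, Public Health Laboratory).

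| Prior results | Meets positive definition | Meets negative definition |
|---|---|---|
| +, + | yes | no |
| +, not done | yes | no |
| not done, + | yes | no |
| −, − | no | yes |
| −, not done | no | yes |
| not done, − | no | yes |
| +, − | yes | yes |
| −, + | yes | yes |

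Only the last two rows overlap, and both need two prior tests that disagree. With one prior result per specimen, the groups are disjoint as written.

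**Size if discordant specimens exist.** Assume the archived label is the reference, that d discordant specimens are filed as negative, and that an otherwise error-free assay detects all of them.

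- Nasopharyngeal specificity = (80 − d)/80
- Pooled specificity = (160 − d)/160
- Nasopharyngeal positive predictive value = 80/(80 + d)

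| d (assumed) | Nasopharyngeal specificity | Exact 95% lower limit | Pooled specificity | Positive predictive value |
|---|---|---|---|---|
| 0 | 100% | 95.5% | 100% | 100% |
| 1 | 98.75% | 93.2% | 99.4% | 98.8% |
| 2 | 97.5% | 91.3% | 98.75% | 97.6% |
| 4 | 95.0% | 87.7% | 97.5% | 95.2% |

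Four such specimens would be 4/80 = 5% of the negative draw. Nothing in the protocol points to a share of that size.

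**Effect on the comparison between assays.** For one specimen detected only by the new assay, the difference (new minus comparator) is +1/80 = +1.25 points of sensitivity if labelled positive, or −1.25 points of specificity if labelled negative. If both assays detect it or both miss it, the difference is 0. The comparison therefore moves only for a specimen that was tested twice, gave discordant results, and also splits the study assays.

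**Would a fixed rule remove the misclassification?** Suppose every specimen with any prior positive is filed as positive. If d of the prior positives were false and an otherwise error-free assay correctly reads them negative, its nasopharyngeal sensitivity is (80 − d)/80. The loss per specimen is the same 1.25 points, now in sensitivity instead of specificity.

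**Scope.** The plural noun in the saliva definitions gives the same strict opening there: two commercial assays could disagree on one saliva specimen. The question is not peculiar to the analysis listed as "Nasopharyngeal specimens only".

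**The case for a change.** The best case for amending is that the overlap is real on the text and nothing in the protocol closes it. Labels are assigned when specimens are retrieved, so a rule written later could upset the 80/80 split. Defining negatives as negative on every prior test would take one sentence and a lookup of prior results, without altering the 320 specimens or the laboratory work.

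The logical point stands, and so does the low cost. Three things keep it from being a defect.

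- The overlap depends on double testing with conflicting results, which no section reports. Sections 5.1 and 7.1 both supply the conjunction that is missing from section 4.1 and the synopsis, so the bare comma is better read as a clerical slip than as evidence that both tests were done.
- Section 7.1 is a retrieval quota under a sample-size heading. That the archived result is also the reference for accuracy is a reasonable inference, but it is not stated, and the method cited in section 4.1 is not at hand.
- The any-positive rule is one choice among several. Excluding discordant specimens or resolving them by further testing is equally defensible, and the any-positive rule moves possible error from specificity to sensitivity.

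**Conclusion.** The concern does not call for a change. Section 7.1 leaves unwritten how to label a specimen whose prior results conflict. This is a small gap that staff holding those results would fill at retrieval, and a choice among reasonable rules. Following the plan as written is not shown to give a wrong answer.

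The effect is nil if no specimen has conflicting prior results. Otherwise it is 1.25 points of nasopharyngeal sensitivity or specificity (0.625 pooled) per specimen, and only for an assay that contradicts the label given. These sizes assume that the archived label is the reference and that the denominators are 80 and 160. The number of affected specimens is unknown and may be zero. The conclusion rests on reading sections 5.1 and 7.1 as one prior result per specimen. If retrieval showed many double-tested specimens with conflicting results, the handling chosen for them would matter more.

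### Positives are chosen on a prior test of unstated target gene; if that target is M, sensitivity leans towards the WHO and CDC assays and M-variant infections are under-represented

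*Protocol*

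**What the plan says.** Protocol section 7.1 plans four groups of 80: "We will perform all 4 RT-PCR assays on a total of 320 specimens". The two positive groups are defined by an earlier result. One is "80 nasopharyngeal specimens which tested positive for influenza A by commercially-available molecular assays or by testing performed at the Public Health Laboratory" (the entry goes on to complete that laboratory's name). The other is "80 saliva specimens which tested positive for influenza A by commercially-available molecular assays". The negative groups mirror these, for example "80 saliva specimens which tested negative for influenza A by commercially-available molecular assays". Section 5.1 admits any specimen with a prior influenza A test from either source. Neither section names the gene that the earlier test targets or asks for it to be recorded.

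Section 2 gives the reason for the study: "recent studies have shown that mutations in the M gene have led to a reduced sensitivity of RT-PCR assay targeting this gene". It also says: "The M gene is often used as the target for all influenza A viruses". The PB2 and NS assays are offered as alternatives. The synopsis states the hypothesis as non-inferiority to the WHO and CDC assays, without a margin. Ct value is the secondary outcome. On size, 7.1 says only: "The sample size is based on feasibility of the study".

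**The concern.** An infection that the earlier test missed cannot be among the 160 positives. If that test targets M, the infections most likely to be missing are those with M mutations, which are the ones that would separate PB2 and NS from the M gene comparators. Random retrieval from the archive does not help, because the group being sampled is already defined by the earlier result.

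The sensitivity comparison could then understate the new assays. A tie would say little about the problem they were designed for. This is settled when specimens are retrieved: no later analysis can restore infections that were never drawn, or stratify by a target gene that nobody recorded.

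**Working it through.** **The plan's own figure.** 4 × 80 = 320, which reproduces. Positives: 80 + 80 = 160. The size rests on feasibility, so there is no power calculation to check.

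**Inputs that the protocol does not give.** These are the earlier test's target, the share of infections with M mutations, and the loss of detection they cause. Every rate below is an assumption, used to show direction and range.

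**Limiting case: complete failure, shared by the earlier M gene test and the M comparators.** Let d be the share of infections in which M detection fails and p the share that PB2 misses, independently.

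- All infections: PB2 minus M = (1 − p) − (1 − d) = d − p.
- Prior-test positives only: (1 − p) − 1 = −p.
- Shift = d, whatever p is.

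With d = 3% and p = 2% in 1,000 infections, M detects 970 and PB2 980, a difference of +1 point. Among the 970 selected, M misses none and PB2 misses 0.02 × 970 = 19.4 (2%), a difference of −2 points. The shift is 3 points. For d from 1% to 5% it is 1 to 5 points, or 1.6 to 8 specimens in 160.

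**Partial failure.** Let v be the M-variant share of infections. Assume 97% sensitivity for every assay on non-variants and for PB2 and NS on variants, and 50% for M gene assays on variants.

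- True gap = v × (97 − 50) points.
- Variant share among positives after selection by an M gene test: v′ = 0.50v / [0.50v + 0.97(1 − v)].
- Observed gap if the M assays fail independently on variants = v′ × 47 points.
- Observed gap if they fail on the same specimens = 0, because the M comparators then detect the selected variants as well as PB2 and NS do.

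| v | True gap | v′ | Observed, same failures | Observed, independent failures | Observed, prior test not M-based |
|---|---|---|---|---|---|
| 2% | 0.94 | 1.0% | 0 | 0.49 | 0.94 |
| 5% | 2.35 | 2.6% | 0 | 1.24 | 2.35 |
| 10% | 4.70 | 5.4% | 0 | 2.55 | 4.70 |
| 20% | 9.40 | 11.4% | 0 | 5.37 | 9.40 |

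Example at v = 10%: v′ = 0.05 / (0.05 + 0.873) = 5.4%, and 0.0542 × 47 = 2.55 points. For the same 5% variant share, the shift is about 5 points with complete shared failure, 2.35 with half-failure that is shared, and 2.35 − 1.24 = 1.11 with half-failure that is independent.

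**Where the missed infections go.** They fall among specimens that tested negative. With influenza prevalence π of 10% to 30% among tested specimens and v of 5% to 20%, the variant share of negatives is 0.50πv / [π(0.50v + 0.03(1 − v)) + (1 − π)]. That is 0.28% to 4.07%, or about 0.4 to 6.5 of the 160 negatives.

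**The case against.** The other side has five good arguments.

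- **The premise is conditional.** The protocol says that M is often the target, not that it was the target here. This stands, so the tilt can be stated only as conditional.
- **A reader might infer that M variants are screened out altogether, that the M comparators start near 100% by construction, and that PB2 and NS can only tie or lose.** The documents do not support this. It needs complete failure on the same specimens by the earlier kit, the WHO assay and the CDC assay. Section 2 speaks of reduced sensitivity, the two comparators are separate published assays, and nothing says the earlier kit shares their primer sites. In the table, 0.49 to 5.37 points of advantage survive when failures are independent.
- **Other signal remains.** A variant that weakens M detection without abolishing it can show as a later M Ct in the same specimen, and Ct is an outcome. The 160 prior negatives are also run on all four assays. Whether PB2 or NS detections there count towards sensitivity depends on the reference standard, which section 4.1 leaves to a cited publication. If it is the prior result, the natural reading of 7.1, they count as false positives.
- **The hypothesis is non-inferiority.** A bias towards M gene comparators works against the new assays, so it would not produce a false success.
- **The reversal from +1 to −2 points depends on the chosen inputs.** It occurs because d was set above zero but p was also kept below d. A deficit of 2 points is about 3 of 160 specimens (3 against 0 discordant: exact McNemar p = 2 × 0.5³ = 0.25).

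What remains is that the plan selects positives on a test whose target is neither stated nor recorded, so neither the direction nor the size of the bias could be judged afterwards.

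**Conclusion.** The point holds in conditional form, as a cheap improvement. Selecting positives on an earlier test biases sensitivity towards assays that share its target. With an M-based test, M-variant infections are depleted and the WHO and CDC assays gain. With an NS or PB2 target, the bias could favour a new assay instead. With no shared target, this tilt is absent.

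The size cannot be derived from the protocol. It is 1 to 5 points for an assumed 1% to 5% dropout under complete, shared failure, and less for the same variant share when failure is partial or not shared. An M-based test puts the study at risk of a false failure of non-inferiority, or of a tie that says nothing about M mutations. A reversed ranking of the assays is a possible extreme and not an expected result.

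**What to change.** - **Sections 5.1 and 7.1:** keep random retrieval, and record for each specimen the prior assay and its target gene where known. Quotas should not be filled by target: that would conflict with random retrieval, and favouring NS- or PB2-based tests could tilt the comparison the other way.
- **Section 7.2:** report the sensitivity of all four assays, and paired Ct differences, separately by prior-test target: M only; shared with PB2 or NS; other or multiple; unknown.
- **Conclusion:** where the positives were selected by an M gene test, limit the sensitivity claim to specimens already detectable by an M gene assay.

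The cost is one field from laboratory records and one more breakdown in the results. No extra specimens are needed. The downside is precision: with every positive detected, the exact 95% lower limit is 97.7% for 160 of 160 but 95.5% for 80 of 80, and smaller strata give wider intervals still. Some kits may not disclose their target, so the unknown stratum could be sizeable.
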